6.2.3 Follow-up Period (84 days±2 days)

During the follow-up period, the investigator should collect AE&SAE information and concomitant therapy by telephone.

Patients who discontinue study treatment early should complete all assessments as soon as possible, which is the same as visit 4, especially, AE check and safety test, such as 12 lead-ECG, Laboratory tests, and so on.

6.2.3.1 Vital status for patients who discontinue early

Patients who withdraw permanently from the randomized treatment period will be followed up by phone regarding their health status until their projected normal exit date from the trial.

The phone calls should be made at approximately 4 and 8 weeks after the patient is randomized. The site must make at least two attempts to contact the patient.

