Dispense patient diary	X	X	X	
Dispense trial identification card (TIC)	X			
Collect Respimat® or Handihaler®			X	X ¹
Collect Rescue Medication		X ⁴	X ⁴	X ⁴
Collect and review patient diary		X	X	X ¹
Adverse events		X	X	X ¹
Compliance check			X	X
Concomitant therapy	X	X	X	X ¹
PASAPQ: question 1-14			X	X
PASAPQ: question 15-16				X
Conclusion of Patient participation				X ¹

1. To be completed by all patients including those who discontinue early because visit 4 is the end of study treatment.
2. Visit 5 is the end of study visit.
3. To be dispensed from Visit 1 to Visit 3.
4. Rescue medication should be collected at next visit whether the patient use or not.
5. At Visit 3, the investigator will instruct the patient how to use first study drug intake on site. To avoid overdosing, the investigator needs to confirm whether the patient has already taken the medication at home on the day of V3 visit. If so, the patient will not take the first dose of the newly assigned treatment at Visit 3.
6. Historical data from spirometry measurements within the past 6 months either at the site or at the other hospital may be used. If the measurements are not performed at the trial site a signed copies of the measurement printouts must be provided to the trial site for source data verification. In case several qualifying spirometry measurements are available, the most recent one should be referred to as long as it was not performed during an exacerbation. Patients may not be randomised to the study without the availability of spirometry data at the actual study site.

TABLE OF CONTENTS

TITLE PAGE	1
CLINICAL TRIAL PROTOCOL SYNOPSIS	2
FLOW CHART	4
TABLE OF CONTENTS	5
ABBREVIATIONS	9
1. INTRODUCTION	11
1.1 MEDICAL BACKGROUND	11
1.2 DRUG PROFILE	11
1.3 RATIONALE FOR PERFORMING THE TRIAL	12
1.4 BENEFIT - RISK ASSESSMENT	13
2. TRIAL OBJECTIVES AND ENDPOINTS	14
2.1 MAIN OBJECTIVES, PRIMARY AND SECONDARY ENDPOINTS	14
2.1.1 Main objectives	14
2.1.2 Primary endpoint(s)	14
2.1.3 Secondary endpoint(s)	14
3. DESCRIPTION OF DESIGN AND TRIAL POPULATION	15
3.1 OVERALL TRIAL DESIGN AND PLAN	15
3.2 DISCUSSION OF TRIAL DESIGN, INCLUDING THE CHOICE OF CONTROL GROUP(S)	15
3.3 SELECTION OF TRIAL POPULATION	15
3.3.1 Main diagnosis for trial entry	16
3.3.2 Inclusion criteria	16
3.3.3 Exclusion criteria	17
3.3.4 Withdrawal of patients from treatment or assessments	18
3.3.4.1 Discontinuation of trial treatment	18
3.3.4.2 Withdrawal of consent to trial participation	19

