3. DESCRIPTION OF DESIGN AND TRIAL POPULATION

3.1 OVERALL TRIAL DESIGN AND PLAN

This is a multicentre, randomised, open-label, two-way cross-over study to compare the patient acceptability/preference between Tiotropium Respimat® and Tiotropium Handihaler®.

Following an initial screening assessment, eligible patients will be randomized to the open-label phase of the trial during which one group of patients will receive 5µg tiotropium (2 puffs of 2.5µg) administered once daily by Respimat® (T1), the other group will receive 18µg tiotropium once daily by Handihaler® (T2) for 4 weeks. After the first 4-week treatment, these two groups of patients will be switched to the second period treatment.

A 8-week, two way cross-over, open-label study

[figure not shown]

Figure 3.1:1 A 8-week, two way cross-over, open-label study

Patients who withdraw prematurely from the randomised treatment period will be followed up regarding COPD exacerbations, SAEs and vital status until their predicted normal exit date from the trial.

Refer to the [Flow Chart](#) (FC) for an overview of procedures to be done at each visit.

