5.2.2 Vital signs

Pulse rate and blood pressure will be measured and recorded at screening Visit 1 and Visit 4.

Vital Status for patients who discontinue early:

The objective of obtaining vital status is to ascertain information on health status in patients who withdraw prematurely from randomized treatment up to the previously projected exit date from the trial. Depending on the time of discontinuation, there will be 1 or 2 calls made to the patients to assess their vital status. The site must make at least 2 attempts to contact the patient at each projected time point. The following information should be obtained during these phone calls: 1) date of follow up; 2) status (alive, deceased or lost to follow up); if lost to follow up, last date known alive, if patient is deceased the date and cause of death must be recorded. In this case the site must complete and forward an SAE form to [REDACTED]

[REDACTED] and the reason for lost to follow up should be recorded.

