6. INVESTIGATIONAL PLAN

6.1 VISIT SCHEDULE

The study will consist of three sequential periods, a Screening period of up to 7 days, a treatment period of 8 weeks and a follow-up period of 4 weeks. The maximum duration is expected to be 93 days.

Following an initial screening, eligible patients will be randomized to enter the first 4-week treatment periods in which they will be given Tiotropium Respimat® or Tiotropium HandiHaler® respectively. Before the treatment phase, patients will be trained to use these two inhalers correctly. After the first treatment period, patients will enter the next 4-week treatment phase and have to switch to the other inhaler. After each of the treatment period, patients will fill-in the performance domain, convenience domain and overall satisfaction. After conclusion of both treatment phases (at visit 4), all patients will indicate their preference and willingness to continue of these two inhalers in the PASAPQ.

Adverse events will be tracked from screening to the follow-up period. All SAEs or any AE associated with trial medication persisting after trial completion must be followed up until they have been resolved or have been fully characterized (have been assessed as “chronic” or “stable”, or no further information can be obtained).

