7.3.4 Safety analyses

All treated patients will be included in the safety analysis. In general, safety analyses will be descriptive in nature and will be based on BI standards. No hypothesis testing is planned. Adverse events will be coded using the Medical Dictionary for Drug Regulatory Activities (MedDRA). Standard BI summary tables and listings will be produced. All adverse events with an onset between start of and end of the REP, a period of 4 weeks after the last dose of trial medication, will be assigned to the on-treatment period for evaluation.

Frequency, severity, and causal relationship of adverse events will be tabulated by system organ class and preferred term after coding according to the current version of the Medical Dictionary for Drug Regulatory Activities (MedDRA) at database lock.

Vital signs (blood pressure and pulse rate), physical examinations, or other safety-relevant data observed at screening, during the course of the trial and at the end-of-trial evaluation will be assessed with regard to possible changes compared to findings before start of treatment.

Laboratory data will be analysed both quantitatively as well as qualitatively. The latter will be done via comparison of laboratory data to their reference ranges. Values outside the reference range as well as values defined as clinically relevant will be summarised. Treatment groups will be compared descriptively with regard to distribution parameters as well as with regard to frequency and percentage of patients with abnormal values or clinically relevant abnormal values.

Frequency, severity, and causal relationship of adverse events will be tabulated by system organ class and preferred term after coding according to the current version of the Medical Dictionary for Drug Regulatory Activities (MedDRA) at database lock.

Vital signs (blood pressure and pulse rate), physical examinations, or other safety-relevant data observed at screening, during the course of the trial and at the end-of-trial evaluation will be assessed with regard to possible changes compared to findings before start of treatment.

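### The dedicated calls to early discontinuers end about four weeks before the exit date to which the protocol promises follow-up, and they omit events it promises to collect

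*Protocol*

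**What the plan says.** **Follow-up promised.** Protocol section 3.1 states that patients who withdraw early from randomised treatment "will be followed up regarding COPD exacerbations, SAEs and vital status until their predicted normal exit date from the trial". Section 6.2.3.1 says that they "will be followed up by phone regarding their health status until their projected normal exit date from the trial". Section 5.2.2 sets the same end date.

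**Exit date.** Flow Chart footnote 2 reads "Visit 5 is the end of study visit". Section 6.1 plans, after screening, "a treatment period of 8 weeks and a follow-up period of 4 weeks", and section 6.2.3 places the follow-up contact at Day 84 ± 2.

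**Calls scheduled.** Section 6.2.3.1 continues: "The phone calls should be made at approximately 4 and 8 weeks after the patient is randomized". Section 5.2.2 says that, depending on when the patient stopped, "there will be 1 or 2 calls made to the patients to assess their vital status". The items it asks for are the date of follow-up, whether the patient is alive, deceased or lost, the last date known alive, and the date and cause of any death.

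**Reduced reporting.** For patients who stop medication and accept further contact but not physical visits, section 5.2.6.2.1 requires deaths, related SAEs and related AESIs that come to the investigator's notice, up to the individual's end of trial.

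**Analysis window.** Section 7.3.4 extends AE assignment over the residual effect period: "a period of 4 weeks after the last dose of trial medication, will be assigned to the on-treatment period for evaluation". SAP sections 6.1 and 7.8.1 use the same 4 weeks (28 days).

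**The concern.** The two statements in section 6.2.3.1 do not agree. Follow-up is to reach the projected exit date, yet the scheduled calls stop at about the end of the treatment period. The call items in section 5.2.2 are also narrower than section 3.1, since they ask for neither exacerbations nor non-fatal SAEs. A site cannot satisfy all of these sections as written.

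What is at stake is safety ascertainment. Section 6.2.4 brings safety information from discontinued patients into the safety analysis, and events in the 4 weeks after the last dose are attributed to treatment. If a site takes the dedicated calls as the whole of follow-up for a patient who stopped in the second period, part of that window has no scheduled contact, while completers have one at Day 84. The primary endpoint is not affected.

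**Working it through.** **1. Exit day, checked against the protocol's own figure.** Screening lasts up to 7 days, follow-up is at Day 84, and the window is 2 days (sections 6.1 and 6.2.3).

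7 + 84 + 2 = 93 days, which is the maximum duration stated in section 6.1. The projected exit is therefore Day 84, range 82 to 86.

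**2. Last dedicated call.** Week 8 is about Day 56. A patient who stops before Day 28 has two calls ahead (Days 28 and 56); one who stops from Day 28 on has one. This fits the one or two calls in section 5.2.2, so that section gives no sign of a later call.

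**3. Gap from last dedicated call to exit.**

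- Nominal: 84 − 56 = 28 days.
- With the Visit 5 window: 82 − 56 = 26 to 86 − 56 = 30 days.

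**4. Residual effect period after the last call.** For last-dose day L the period ends on Day L + 28, so the days after the call are max(0, L + 28 − 56).

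| Last dose (day) | Residual period ends (day) | Days after the week-8 call |
|---|---|---|
| 28 or earlier | 56 or earlier | 0 |
| 29 | 57 | 1 |
| 35 | 63 | 7 |
| 42 | 70 | 14 |
| 49 | 77 | 21 |
| 55 | 83 | 27 |

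A last dose on Day 56 is scheduled completion, so 27 days is the most that an early stopper can have. The call days are approximate in the protocol, and these figures shift day for day with the actual call.

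**5. Content, side by side.**

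| Section | Whom it covers | What is collected |
|---|---|---|
| 3.1 | Early withdrawers | Exacerbations, SAEs, vital status |
| 6.2.3.1 | Permanent withdrawers from treatment | Health status, undefined, under a vital-status heading |
| 5.2.2 | Early withdrawers | Vital status; date and cause of death |
| 5.2.6.2.1, general rule | All patients | All AEs and AESIs to the individual's end of trial |
| 5.2.6.2.1, vital-status rule | Discontinuers declining physical visits | Deaths, related SAEs and related AESIs that become known |
| 6.2.3 | Not stated for the telephone contact | AEs, SAEs, concomitant therapy |

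The vital-status rule in section 5.2.6.2.1 leaves out unrelated non-fatal SAEs, and exacerbations that are not related SAEs. Section 3.1 promises both.

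**The case against.** The strongest reply is that other sections already cover the gap. Section 6.2.3, the parent of 6.2.3.1, has AE and SAE information collected by telephone in the follow-up period and does not exclude early discontinuers. Section 3.3.4.1 keeps a patient who stops treatment in the trial, with flow-chart follow-up if he or she agrees. Section 5.2.6.2.1 collects all AEs to the individual's end of trial, and section 6.1 tracks them into follow-up. Worsening of the underlying disease is itself an AE under section 5.2.6.1.1, so exacerbations fall within that general collection.

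This stands, and it rules out a stronger reading. A reader might infer that every early stopper loses four weeks of safety follow-up and that event counts are therefore biased low. The documents support neither: the loss is a risk under one reading of the rules, the safety analysis is descriptive, and nothing in the documents shows that early stoppers have more events. A reader might also take the 15% allowance (0.15 × 71 = 10.65, about 11 patients) as the number affected. Section 7.7 gives that allowance for patients without evaluable data, so it is not a discontinuation rate.

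The reply does not remove the conflict. Section 6.2.3 turns to early discontinuers in a separate paragraph, asking for Visit 4 assessments as soon as possible, and then gives them their own call schedule. It does not say whether the later telephone contact also applies. The narrower reporting rule for patients who decline visits remains in either case.

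**Conclusion.** The contradiction is real and worth correcting, although it is limited to safety follow-up. The last dedicated call comes about 28 days (26 to 30) before the exit date, and its listed content is narrower than section 3.1. The practical exposure is confined to patients followed only by these calls, notably those who decline physical visits. For them, 1 to 27 days of the residual effect period fall after the last call if the last dose was on Day 29 to 55, and none if it was by Day 28. The documents do not say how many such patients to expect.

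This assumes that the projected exit is Visit 5 at Day 84. Section 6.2.2 lists the conclusion of participation at Visit 4, which early discontinuers also undergo. If Day 56 were the exit, the timing gap would be zero. Footnote 2, sections 6.1 and 6.2.3, and the 93-day total favour Day 84. The Visit 5 column of the Flow Chart is not legible in the text available, so its entries could not be checked.

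**What to change.** Reconcile Protocol sections 3.1, 5.2.2, 5.2.6.2.1, 6.2.3 and 6.2.3.1 on three matters: when early discontinuers are contacted, what is asked, and which patients each rule covers. The scheduled contacts should match the follow-up end date and the events that the protocol already promises. State expressly whether the follow-up telephone contact in section 6.2.3 applies to patients who stop early, including those who decline physical visits, and what counts as the individual end of trial for them.

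The cost is wording in these sections and, because the Day 84 telephone contact already exists, at most one extra call for a few patients.

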6.2.4 Removal of patients from therapy assessment

Criteria and rules for stopping subject treatment

To be considered complete, a patient must complete the use of both devices as specified in the protocol without violations of the protocol significant enough to obscure the patient acceptability/preference. Patients who fail to complete all treatment will not be replaced.

Dropouts and Withdrawals

Randomized patients who fail to complete all treatment and all of the testing as specified in the protocol will not be considered complete, may not be enrolled at a later date and will not be replaced. If the investigator feels a subject should be discontinued, the Local Clinical Monitor should be contacted.

A record will be kept of all patients who fail to complete all test-days and their reasons for discontinuation. A final physical examination should be conducted on all discontinued patients. All safety information collected from discontinued patients will be included in the safety analysis of the study.

7. STATISTICAL METHODS AND DETERMINATION OF SAMPLE SIZE

Details of all analyses will be provided in the Trial Statistical Analysis Plan (TSAP).

7.1 STATISTICAL DESIGN - MODEL

This is a multi-center, randomized, open-label, two-way cross-over study to investigate the patient acceptability/preference of Tiotropium Respimat® compared with Tiotropium Handihaler® in patients with moderate to severe chronic obstructive pulmonary disease (COPD).

Based upon these design considerations, the primary endpoint (performance domain of PASAPQ) will be analysed using Mixed-effects Model for Repeated Measures (MMRM), with treatment and period as fixed effects, and patient as a random effect. Compound symmetry will be used as a covariance structure for within-patient variation.

7.2 NULL AND ALTERNATIVE HYPOTHESES

The following hypothesis (two-sided $\alpha = 0.05$) will be tested for the primary endpoint – performance domain of PASAPQ after 4 weeks of treatment:

H_0 : mean performance score for Tiotropium Respimat® = mean performance score for Tiotropium Handihaler®

H_a : mean performance score for Tiotropium Respimat® \neq mean performance score for Tiotropium Handihaler®

7.3 PLANNED ANALYSES

The analysis will be based on the following populations:

- Treated set (TS) is defined as all patients who were dispensed study medication and were documented to have at least one dose of investigational treatment.
- Full analysis set (FAS) is defined as all patients who were randomized to treatment sequence and received at least one dose of one study drug and providing at least one PASAPQ score measurement.

The primary endpoint will be analyzed on the FAS (as the primary analysis). The secondary endpoints will be analyzed on the FAS.

Safety analyses will be performed on the TS.

[figure not shown]
Demographic and baseline characteristics will be analyzed on the TS using descriptive statistics.

7.3.1 Primary endpoint analyses

In the primary analysis, comparisons between treatment groups for the performance domain of PASAPQ will be based on a mixed effect repeated measures model (MMRM). This model will include treatment and period as fixed effects and patient as a random effect. Compound symmetry will be used as a covariance structure for within-patient variation. The SAS procedure MIXED will be used involving the restricted maximum likelihood estimation and the Kenward-Roger approximation for denominator degrees of freedom (Kenward, 2010). Adjusted mean values as well as treatment contrasts will be presented together with the 95% confidence intervals (CI) and p-values.

7.3.2 Secondary endpoint analyses

Continuous secondary endpoints will be analysed using a similar MMRM model as for the primary endpoint. Chi-squared test will be performed to analyse proportion of patients indicating preference.

7.3.4 Safety analyses

All treated patients will be included in the safety analysis. In general, safety analyses will be descriptive in nature and will be based on BI standards. No hypothesis testing is planned. Adverse events will be coded using the Medical Dictionary for Drug Regulatory Activities (MedDRA). Standard BI summary tables and listings will be produced. All adverse events with an onset between start of and end of the REP, a period of 4 weeks after the last dose of trial medication, will be assigned to the on-treatment period for evaluation.

Frequency, severity, and causal relationship of adverse events will be tabulated by system organ class and preferred term after coding according to the current version of the Medical Dictionary for Drug Regulatory Activities (MedDRA) at database lock.

Vital signs (blood pressure and pulse rate), physical examinations, or other safety-relevant data observed at screening, during the course of the trial and at the end-of-trial evaluation will be assessed with regard to possible changes compared to findings before start of treatment.

Laboratory data will be analysed both quantitatively as well as qualitatively. The latter will be done via comparison of laboratory data to their reference ranges. Values outside the reference range as well as values defined as clinically relevant will be summarised. Treatment groups will be compared descriptively with regard to distribution parameters as well as with regard to frequency and percentage of patients with abnormal values or clinically relevant abnormal values.

Frequency, severity, and causal relationship of adverse events will be tabulated by system organ class and preferred term after coding according to the current version of the Medical Dictionary for Drug Regulatory Activities (MedDRA) at database lock.

Vital signs (blood pressure and pulse rate), physical examinations, or other safety-relevant data observed at screening, during the course of the trial and at the end-of-trial evaluation will be assessed with regard to possible changes compared to findings before start of treatment.

Laboratory data will be analysed both quantitatively as well as qualitatively. The latter will be done via comparison of laboratory data to their reference ranges. Values outside the reference range as well as values defined as clinically relevant will be summarised. Treatment groups will be compared descriptively with regard to distribution parameters as well as with regard to frequency and percentage of patients with abnormal values or clinically relevant abnormal values.

7.3.5 Pharmacokinetic and pharmacodynamic analyses

No pharmacokinetic analysis is planned for this study.

7.4 INTERIM ANALYSES

No interim analysis is planned.

7.5 HANDLING OF MISSING DATA

Every effort should be made to collect the complete data at the planned time points for this trial.

For PASAPQ, imputation of responses to individual questions will follow the “half-scale rule”. If a patient missed less than four of the seven questions in the Performance domain or less than four of the six questions in the Convenience domain in the PASAPQ, then the missing item in this domain is imputed using the observed mean from the same domain, and then the Total score is calculated as the sum of the 13 items after substitution for missing items at the domain level has taken place. If a patient missed more than three items in either domain, then the domain and the Total score are set to missing and will not be imputed.

The number of patients who cannot be included in the FAS will be summarised by treatment group and period. Sensitivity analyses, in which missing data will be imputed according to the reason they are missing, will be described in the TSAP.

